9.3 Procedures at each visit

Inclusion visit – day 0

- Inclusion/Exclusion Criteria
- Patient Information and Informed Consent
- Demographics
- Relevant Medical History

- Vital Signs/Clinical Examination
- Laboratory Results
- Naso-pharyngeal swab
- Sputum collection if possible
- According to study arm:
 - Venous blood sampling
 - POCT PCT measurement
 - Lung ultrasound
- Antibiotic prescription

Telephone visit – day 07

- Duration of the episode
- Clinical failure
- Adverse effects of antibiotics
- Duration of antibiotic therapy
- Compliance to antibiotic therapy
- Additional visits
- Additional antibiotic prescription
- Adverse Outcomes
- Consultation process

Telephone visit – day 28

- Duration of the episode
- Clinical failure
- Adverse effects of antibiotics
- Additional visits
- Additional antibiotic prescription
- Adverse Outcomes
- Satisfaction of the patient

10. SAFETY

10.1 Definition and assessment of (serious) adverse events and other safety related events

Only Serious Adverse Events will be recorded as part of this trial, defined according to article 63 of the OCLIN. as any event that:

- results in death,
- is life-threatening,
- requires in-patient treatment not envisaged in the protocol or extends a current hospital stay.
- results in permanent or significant disability/incapacity
- causes a congenital anomaly or birth defect.

Relationship with the intervention will be graded as probable, possible or unlikely, based on the definitions of WHO-UMC and the criteria listed in the ICH E2A guidelines

10.2 Reporting of serious adverse events (SAE) and other safety related events

If serious adverse events occur, and it cannot be excluded that the events are attributable to the intervention under investigation, the GP must document them in a standardised manner. In addition, the GP shall report these events to the Principal-Coordinating investigator within 24 hours, who will report them to the competent ethical committee within 15 days.

10.3 Follow up of (Serious) Adverse Events

SAEs will be followed by the GP until resolution or stabilisation. Occurrence of a SAE (apart from death) will not lead to study withdrawal. Participants with ongoing SAEs at study termination will be further

followed up until recovery or until stabilisation of the disease after termination.

11. STATISTICAL METHODS

This is a randomized clinical trial aiming to show a significant reduction of antibiotic prescription using the UltraPro algorithm.

11.1 Hypothesis

The null hypothesis is that there is no difference in the proportion of antibiotic prescription in patients enrolled in the different arms of the trial.

The alternative hypothesis is that combined use of POCT procalcitonin testing with lung ultrasound leads to significant reduction in antibiotic use with no difference in terms of clinical outcome, duration of the episode, activities restrictions and adverse outcomes.

A reduction of at least 15% in the proportion of patients treated with antibiotics by day 28 is expected as below this threshold, the intervention would be considered as no having a sufficient impact to warrant its implementation at larger scale, at least in its present format.

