11.2 Determination of Sample Size

The sample size was calculated to assess a decrease in antibiotic prescription of at least 15% between the UltraPro and the PCT arms as well as 15% between the PCT arm and usual care.

The proportion of patients receiving antibiotics with the usual care is estimated to be around 60% and to decrease to 45% using PCT and to 30% combining PCT and ultrasound. These numbers have been extrapolated from the subgroup of patients with LRTI in a study at primary care level in the Netherlands [3].

A study sample of 14 GPs and 15 patients per GP in each arm (210 patients per arm and a total of 630 patients) gives a power of 80% to detect a decrease in antibiotic prescription from 60% (usual care) to 45% (PCT), and from 45% (PCT) to 30% (UltraPro), with 5% level of significance, when adjusting for clustering at practice level (intracluster coefficient 0.06) [3]. This sample size guarantees a power of 80% to prove non-inferiority in terms of duration of activities restriction (non-inferiority margin=1 day, standard deviation=4 days) as well as of composite adverse outcome (probability in the “usual care” arm 0.05 with a non-inferiority margin of 0.02). Simulations used to determine the sample size are shown in the following figures.

[figure not shown]

Figure 4: Statistical simulations used to determine sample size

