11.4 Planned Analyses

Datasets to be analysed, analysis populations

The analysis will be performed in intention to treat (pragmatic trial). The analysis population will comprise all patients included by the randomised GPs. The primary analysis will include all patients enrolled in the study, irrespective of follow-up. Patients who are lost to follow-up will be considered as having had a clinical failure, an adverse outcome and duration of disease equal to the maximum duration measured in the other patients. Patients in whom GPs did not follow the respective algorithm recommendation and/or who did not have complete telephone follow-up will be excluded from the per-protocol analysis.

Primary Analysis

Odds ratio of antibiotic prescription between 2 groups as well as the difference in proportion of patients prescribed an antibiotic by day 28 using logistic regression corrected for variation at the GP level (generalized linear mixed effect)

Secondary Analyses

The following statistical analyses are planned:

- Difference between the mean number of days with restricted activities by day 14 using linear mixed effect regression
- Difference between the mean number of medical consultations by day 28 using linear mixed effect regression
- Odds ratio of adverse outcome between 2 groups as well as the difference in proportion of patients with adverse outcome and clinical failure using logistic regression corrected for variation at the GP level (generalized linear mixed effect)
- Difference between the mean daily symptom scores measured in the different arms. The effects of the interventions on recovery will be studied by comparing the slopes of symptom scores over time between arms
- Difference in the mean duration of total time spent in the practice using linear mixed effect regression
- Difference in levels of satisfaction of providers and of patients between arms
- Difference in the mean cost per arm using linear mixed effect regression
- Diagnostic performance of:
 - individual host biomarker(s) based on crude positive and negative likelihood ratios, and on the area under the curve of receiver operator characteristic (ROC) curves, to predict the development of a life-threatening disease, clinical failure, or the presence of pneumonia (using a clinical diagnosis).

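### Section 11.1 claims no difference in clinical outcomes and 11.2 sets two non-inferiority margins, but 11.4 gives no rule for concluding non-inferiority

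*Combined protocol and SAP*

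**What the plan says.** Section 11.1 makes the absence of clinical harm part of the alternative hypothesis, alongside the fall in prescribing: the combined strategy "leads to significant reduction in antibiotic use with no difference in terms of clinical outcome, duration of the episode, activities restrictions and adverse outcomes".

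Section 11.2 sizes the trial on antibiotic prescription and adds a secondary statement for two clinical outcomes. It claims "power of 80% to prove non-inferiority in terms of duration of activities restriction (non-inferiority margin=1 day, standard deviation=4 days", and the same power for the composite adverse outcome, with a usual-care probability of "arm 0.05 with a non-inferiority margin of 0.02". The sample is 14 GPs with 15 patients each, 210 per arm.

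Section 11.4, Secondary Analyses, plans a difference in mean days of restricted activity from a linear mixed model. For the binary outcomes it plans "Odds ratio of adverse outcome between 2 groups as well as the difference in proportion of patients with adverse outcome and clinical failure", from a logistic mixed model. The synopsis lists the same kind of analyses. Neither place mentions non-inferiority, a margin, a confidence limit, an error rate for non-inferiority, or which pair of arms is compared. Section 11.4 defines a per-protocol set but gives it no role in a non-inferiority conclusion. No margin is given anywhere for day-7 clinical failure or episode duration.

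**The concern.** A hypothesis of no difference cannot be supported by failing to find one. It needs a margin and a confidence limit that excludes it. The margins are in 11.2, but the analysis section does not use them. That leaves open how the safety half of the conclusion will be reached, including whether a non-significant comparison will be taken as enough.

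The stakes are considerable. Section 3.4 names wrongly withholding antibiotics from patients with pneumonia as a potential risk. Section 1.6 provides no data safety monitoring committee, and 11.3 sets no statistical stopping criterion. The final clinical comparison therefore carries much of the safety claim. Section 13 foresees that favourable results would feed into guidelines and discussions on insurance coverage.

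**Working it through.** **Inputs.** From 11.2: 210 per arm; margin 1 day, SD 4 days; usual-care adverse outcome 0.05, margin 0.02; 5% significance, sidedness not stated; intracluster coefficient 0.06, stated for prescription; 15 patients per GP.

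**Assumptions.** The design effect (DE) is 1 + (15 - 1) x 0.06 = 1.84 if the prescription coefficient also holds for the clinical outcomes, and 1 if there is no clustering. The non-inferiority error rate is taken as one-sided 2.5% or 5%. All figures use the normal approximation, with Phi the standard normal distribution function.

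**Step 1: the plan's own 80%.** With no true difference, power = Phi(margin/SE - z), z = 1.96 or 1.645.

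- Restricted activity: SE = sqrt(DE x 2 x 4²/210) = 0.390 (DE 1) or 0.530 (DE 1.84).
- Composite: SE = sqrt(DE x 2 x 0.05 x 0.95/210) = 0.0213 or 0.0289.

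| Outcome | DE | One-sided 2.5% | One-sided 5% |
|---|---|---|---|
| Restricted activity | 1 | 72.6% | 82.0% |
| Restricted activity | 1.84 | 47.2% | 59.6% |
| Composite | 1 | 15.4% | 24.1% |
| Composite | 1.84 | 10.3% | 17.1% |

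The 80% is approached for restricted activity only at one-sided 5% without clustering. For the composite, no combination comes near it when the true rates are equal. At one-sided 2.5% without clustering, power reaches 79.9% only if the true intervention rate is 2% against 5%, a benefit that 11.2 does not state. For 80% power at equal rates, one-sided 2.5%, the composite needs (1.96 + 0.842)² x 2 x 0.05 x 0.95/0.02² = 1,865 per arm before clustering, and 1,865 x 1.84 = 3,432 with it.

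**Step 2: what a difference test would show under real harm.** The chance of a non-significant two-sided 5% test is 1 - [Phi(d/SE - 1.96) + Phi(-d/SE - 1.96)], where d is the true difference. For the composite, SE = sqrt(DE x (0.05 x 0.95 + p(1 - p))/210), with p the intervention rate.

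| True harm | SE (DE 1; 1.84) | Non-significant (DE 1; 1.84) |
|---|---|---|
| Composite 7% v 5% (at the margin) | 0.0232; 0.0314 | 86%; 90% |
| Composite 10% v 5% (doubled) | 0.0256; 0.0347 | 50%; 70% |
| Restricted activity +1 day (at the margin) | 0.390; 0.530 | 27%; 53% |

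A rule that compares the upper confidence limit with the margin would pass harm exactly at the margin only 2.5% of the time (one-sided 2.5%) or 5% (one-sided 5%).

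**Step 3: what the composite can show at this size.** If both arms had an observed rate of exactly 5%, the upper limit of the two-sided 95% interval would be 1.96 x 0.0213 = 4.2 points, or 1.96 x 0.0289 = 5.7 points with clustering. Both exceed the 2-point margin.

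**The case against.** The strongest reply is that 11.4 lists estimates, not verdicts. It names no p-value rule for these outcomes and never says that non-significance means safety. That is correct, so a reader who infers that the plan equates the two goes beyond the text. What stands is that 11.1 makes the claim and nothing says how it will be reached.

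Four other strong readings also fail. A reader might infer that the trial was sized for non-inferiority, but 11.2 and the synopsis calculate the sample on prescription. A reader might object that an odds ratio cannot be set against an absolute margin, but 11.4 also plans the difference in proportions, which can be. A reader might say that finding no difference is the likely result for every outcome whether or not there is harm. That fits the composite, but a true 1-day excess in restricted activity would be detected 47-73% of the time. And episode duration is not ignored: 11.4 plans symptom-score slopes and a rule for duration in lost patients, although it lists no comparison of day counts.

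The scenarios in the working also leave out the 11.4 rule that counts lost patients as adverse outcomes, which would raise the event rates. The documents give no dropout rate, so this cannot be sized. Figure 4, with the sponsor's simulations, is not in the text available, so their settings cannot be checked.

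**Conclusion.** The gap is real. A claim of no clinical difference is part of the alternative hypothesis and margins exist for two outcomes, but no decision rule connects them. If non-significance were used to fill the gap, composite harm at the sponsor's own margin would go unflagged in about nine trials out of ten, and a 1-day harm in restricted activity in roughly a quarter to a half. These ranges rest on the normal approximation and on design effects from 1 to 1.84, the latter borrowing the prescription coefficient. The conclusion for the composite is the same at both ends.

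The primary outcome and its analysis are unaffected. A rule alone will not rescue the composite claim, because 210 per arm gives it low power to show non-inferiority.

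**What to change.** **Section 11.1.** Replace the claim of no difference by non-inferiority on restricted activity and on the composite adverse outcome. Report the other clinical outcomes, including clinical failure and episode duration, as estimates with confidence intervals and no equivalence claim.

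**Section 11.4.** Conclude non-inferiority only if the upper limit of the two-sided 95% confidence interval for the absolute difference, from the GP-level mixed model, is below 1 day or 0.02 respectively. Apply this to UltraPro minus usual care and to PCT minus usual care. Otherwise report that non-inferiority was not shown. State that non-significance is not evidence of no difference. Repeat the analysis in the per-protocol set already defined.

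**Reconcile first.** The restricted-activity window is day 7 in the synopsis and day 14 in 11.4. Unreachable patients are excluded from the safety analysis in 7.2 but counted as clinical failures and adverse outcomes in 11.4. Until both are settled, the rule has no fixed endpoint or population.

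**Section 11.2.** Restate the non-inferiority power with its error rate and clustering assumption. Under the two-sided 95% rule it is 10-15% for the composite and 47-73% for restricted activity; one-sided 5% raises the upper ends to 24% and 82%.

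**Cost.** A few sentences and no new data. The real price is that non-inferiority on the composite will probably not be shown, and the report will have to say so.

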11.2 Determination of Sample Size

The sample size was calculated to assess a decrease in antibiotic prescription of at least 15% between the UltraPro and the PCT arms as well as 15% between the PCT arm and usual care.

The proportion of patients receiving antibiotics with the usual care is estimated to be around 60% and to decrease to 45% using PCT and to 30% combining PCT and ultrasound. These numbers have been extrapolated from the subgroup of patients with LRTI in a study at primary care level in the Netherlands [3].

A study sample of 14 GPs and 15 patients per GP in each arm (210 patients per arm and a total of 630 patients) gives a power of 80% to detect a decrease in antibiotic prescription from 60% (usual care) to 45% (PCT), and from 45% (PCT) to 30% (UltraPro), with 5% level of significance, when adjusting for clustering at practice level (intracluster coefficient 0.06) [3]. This sample size guarantees a power of 80% to prove non-inferiority in terms of duration of activities restriction (non-inferiority margin=1 day, standard deviation=4 days) as well as of composite adverse outcome (probability in the “usual care” arm 0.05 with a non-inferiority margin of 0.02). Simulations used to determine the sample size are shown in the following figures.

[figure not shown]

Figure 4: Statistical simulations used to determine sample size

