Number of Participants, with Rationale:	
We plan to include a total of 630 patients in the study. They will be recruited by 42 GPs, with each GP recruiting 15 patients (210 patients per arm).
 
The sample size was calculated to be able to measure a decrease in antibiotic prescription of at least 15% between UltraPro and PCT arms as well as 15% between PCT arm and usual care. This study sample gives a power of 80% to detect a decrease in antibiotic prescription between 60% (usual care) and 45% (PCT), and between 45% (PCT) and 30% (UltraPro), with 5% level of significance, when adjusting for clustering at practice level (intracluster coefficient 0.06). These numbers have been extrapolated from a study at primary care level in the Netherlands [3].

Study Duration:	20 months (5 months for the pilot study, 15 months for the randomized trial)
Study Schedule:	September 2017 to April 2019

Investigator(s):	
[name] Sponsor-Coordinating investigator Infectious Diseases Service, Lausanne University Hospital [name] [contact]
 
PD [name] Local Principal Investigator Institute for Infectious Diseases, University Bern [name]
 
[name] Co-Investigator Institute of Family Medicine, Lausanne University Hospital [name]
 
[name] Co-Investigator Department of Outpatient Care and Community Medicine, Lausanne University Hospital [name]
 
[name] Study Coordinator, Co-Investigator Infectious Diseases Service, Lausanne University Hospital [name] [contact]
 
[name] Co-Investigator Radiology Service, Lausanne University Hospital [name]
 
[name] [name] Co-Investigator Institute of Family Medicine, Lausanne University Hospital [name]
 
[name] Co-Investigator Institute of Family Medicine, Lausanne University Hospital [name]

-------------------------	--

Study Centre(s):	Service des Maladies Infectieuses Centre Hospitalier Universitaire Vaudois [name]

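### The stated 80% power does not follow from the written inputs: 14 GPs × 15 patients per arm at an intracluster coefficient of 0.06 gives about 63% (60% vs 45%) and 66% (45% vs 30%)

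*Combined protocol and SAP*

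**What the plan says.** Section 11.2 gives the design as "A study sample of 14 GPs and 15 patients per GP in each arm (210 patients per arm and a total of 630 patients"). It says this size "gives a power of 80% to detect a decrease in antibiotic prescription from 60% (usual care) to 45% (PCT"). The same power is claimed for PCT against UltraPro, with assumed rates of 45% and 30%. Both claims are made at a 5% significance level, "when adjusting for clustering at practice level (intracluster coefficient 0.06"). The synopsis (Number of Participants) has the same design, "They will be recruited by 42 GPs, with each GP recruiting 15 patients (210 patients per arm"), and the same claim: "This study sample gives a power of 80% to detect a decrease in antibiotic prescription between 60% (usual care) and 45% (PCT").

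Section 11.2 attributes the figure to simulation: "Simulations used to determine the sample size are shown in the following figures". That figure (Figure 4) does not appear in the text available for this review. The primary analysis in section 11.4 compares arms "using logistic regression corrected for variation at the GP level (generalized linear mixed effect"). Neither section 11.2 nor the synopsis says whether the 5% level is one- or two-sided, or on which scale the 0.06 is defined. Section 11.1 states the null as no difference between arms.

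**The concern.** Every quantity needed for a standard cluster-trial power calculation is printed, so the 80% can be checked directly. It does not come out. An intracluster coefficient of 0.06 with 15 patients per GP nearly doubles the variance, and 210 patients per arm cannot absorb that for a 15-point difference.

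The sample size was built on the two adjacent-arm contrasts. PCT vs UltraPro is the only comparison that isolates what ultrasound adds to procalcitonin. Section 11.1 treats 15 points as the smallest reduction that would justify wider use. If power is lower than stated, a non-significant adjacent-arm result could be read as evidence that a step adds nothing, when the trial had a sizeable chance of missing a real 15-point effect.

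**Working it through.** **Inputs (section 11.2 and synopsis).** 14 GPs per arm; m = 15 patients per GP; n = 210 per arm; 60%, 45% and 30%; 5% level; intracluster coefficient ρ = 0.06. Base case: two-sided test, ρ on the proportion scale (the usual meaning of the term), equal cluster sizes, no adjustment for multiple comparisons.

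**Design effect.** 1 + (m − 1)ρ = 1 + 14 × 0.06 = 1.84. Effective n = 210 / 1.84 = 114.1 per arm.

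**Power**, from Φ(|p₁ − p₂| / SE − 1.96), with SE = √{[p₁(1 − p₁) + p₂(1 − p₂)] / 114.1}:

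- 60% vs 45%: SE = √[(0.2400 + 0.2475) / 114.1] = 0.0654; 0.15 / 0.0654 = 2.295; power = Φ(0.335) = 63.1%.
- 45% vs 30%: SE = √[(0.2475 + 0.2100) / 114.1] = 0.0633; 0.15 / 0.0633 = 2.369; power = Φ(0.409) = 65.9%.
- 60% vs 30%: SE = 0.0628; 0.30 / 0.0628 = 4.78; power = 99.8%.

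**Attempts to reproduce 80%.**

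| Reading | 60 vs 45 | 45 vs 30 |
|---|---|---|
| ρ = 0.06, two-sided, unpooled variance | 63.1% | 65.9% |
| same, pooled variance | 62.3% | 65.0% |
| same, t on 26 df | 59.9% | 62.6% |
| planned mixed logistic model, simulated, two-sided | 64% | 68% |
| ρ = 0.06, one-sided 5%, unpooled | 74.2% | 76.6% |
| planned mixed logistic model, simulated, one-sided | 75.3% | 79.5% |
| 0.06 as latent-scale coefficient, two-sided | 67.8% | 71.3% |
| 0.06 as latent-scale coefficient, one-sided | 78.1% | 81.0% |
| 0.06 as logit-scale random-intercept variance, two-sided | 81.1% | 83.8% |
| no clustering, two-sided, pooled | 87.1% | 89.1% |

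Notes on the table:

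- The two mixed-model rows use beta-binomial data with a proportion-scale coefficient of 0.06, 14 GPs against 14, and 15 patients per GP. The one-sided row uses 1,200 runs and a likelihood-ratio test. The two-sided figures were obtained both that way and with 4,000 runs and a Wald test. The Wald z test had a type I error of 6.9% at 45% vs 45%, so it slightly flatters the power.
- Latent-scale reading: logit variance = (0.06 / 0.94) × π²/3 = 0.21, which is a proportion-scale coefficient of 0.041 to 0.047.
- Logit-variance reading: the proportion-scale coefficient is 0.0140 at 60%, 0.0144 at 45% and 0.0123 at 30%. Simulating the mixed model under this reading (2,000 runs) gives 81.4% and 82.8%.
- Reading 0.06 as a between-GP coefficient of variation overshoots: 83–86% and 86–88%.

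**Working backwards.** By the same unpooled formula, 80% power with 210 per arm needs ρ of about 0.017 (60 vs 45) and 0.023 (45 vs 30) two-sided, or 0.041 and 0.048 one-sided. At ρ = 0.06 two-sided, 80% power corresponds to differences of 18.2 points (60% to 41.8%) and 17.5 points (45% to 27.5%). For scale, 80% power for 15 points at ρ = 0.06 would take about 20 to 22 GPs per arm, depending on the contrast and the variance formula, against the planned 14.

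**The case against.** The strongest reply is that the 80% came from simulations in a figure this review could not see. That figure may state the test, its sidedness and the scale of the 0.06. A logit-scale variance is a natural input when simulating a mixed logistic model, and under that reading the power stands and only the label is wrong. This is a fair limit on what can be concluded: the review cannot say which item is in error. It does not rescue the text, because a reader of section 11.2 or the synopsis is told that 0.06 is an intracluster coefficient.

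A second reply is that the aim is worded as a decrease, so the 5% may be one-sided. With 0.06 taken as printed, that narrows the gap without closing it: 74% and 77% by formula, 75% and 79.5% in the two-arm simulation. A simulation fitting all three arms jointly (600 runs, Wald z, Monte Carlo error about 1.7 points) gave 79% and 77% one-sided and 68% and 66% two-sided. The Wald z test is somewhat optimistic, and both one-sided figures still fall short. A null of no difference with an unqualified 5% level is also conventionally read as two-sided.

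Third, UltraPro vs usual care has over 99% power, and a global three-arm test has about 99%. That stands, and it limits the consequence to the adjacent-arm contrasts. Those are, however, the contrasts on which section 11.2 bases the size.

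**Conclusion.** The point holds. On the written inputs, with a two-sided 5% test and a proportion-scale coefficient, power is about 63% and 66% rather than 80%. The chance of missing a true 15-point reduction is then about 37% (usual care vs PCT) and 34% (PCT vs UltraPro), not 20%. If instead the 0.06 was a logit-scale variance, the 80% is sound but the trial was planned for a proportion-scale coefficient of 0.012 to 0.014, roughly a quarter or less of the clustering the text reports. In either case a statement in section 11.2 and the synopsis needs correcting.

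The mismatch is certain as the text stands; its cause is not, because Figure 4 was unavailable and sidedness is unstated. The calculation assumes exactly 14 GPs per arm and 15 patients per GP. Simple randomisation of 42 GPs does not guarantee 14 per arm, and unequal cluster sizes would lower power further, but the conclusion does not depend on either.

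**What to change.** Check the simulation inputs behind Figure 4. Then, in section 11.2 and the synopsis, state the sidedness of the test and the scale of the 0.06, and apply whichever case is true:

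- **Proportion-scale coefficient, two-sided test:** restate power as about 63% and 66% (over 99% for 60% vs 30%), or state 80% power for differences of about 18 points (60% to 42%) and 17.5 points (45% to 27.5%).
- **Logit-scale random-intercept variance:** correct the label and give the implied proportion-scale coefficient, about 0.012 to 0.014.
- **Latent-scale coefficient with a one-sided test:** say so, and carry the one-sided test into the primary analysis in section 11.4.

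The cost is one check of the simulation inputs and revised wording in two places (also section 11.4 if the test was one-sided), and possibly a less favourable stated power. It requires no extra patients.

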6.2 Randomized Intervention Study

General study design and justification of design

This is a pragmatic cluster randomized controlled clinical trial investigating a new algorithm combining PCT measurement and lung ultrasonography results for the management of LRTIs among adults in GPs practices. Every consecutive patient meeting the inclusion criteria will be included in the study. All patients will be evaluated by the GP at the time of enrolment (day 0) and will have follow-up evaluations on day 7 and 28 via a phone interview by the study team to ask for the presence of LRTI symptoms, of side effects from antibiotics, secondary antibiotic use, number of follow-up visits, secondary hospitalization or death (Figure 2). In case of clinical deterioration, the patient will have a follow-up evaluation at any time, if possible with the same GP. We plan to enrol patients for a period of 15 months to reach the estimated sample size.

Methods of minimising bias

The study will be randomized. To avoid contamination between arms, randomization will be performed at GP level and only one GP per practice will be included. The cluster effect related to GP was taken into account while calculating the sample size and the outcome measures.

Details concerning GPs recruited in the study will be entered in a database using REDCap[©]. The randomization module of the REDCap software will then be used to attributed each of the GPs to one of the three study arms. We will perform a simple randomization using a 1:1:1 ratio.

[figure not shown]

Figure 2: Study design of the randomized intervention study

Study Setting

This study will be carried out in GPs practices located in different Swiss regions to ensure a representation of different cultural areas (German-speaking part (Bern) and French-speaking part of Switzerland (Vaud, Neuchâtel, Fribourg, Valais and Jura)). Each participating GP will be responsible to enrol consecutive eligible patients (total of 15 patients) in the study

These regions have been chosen because of good collaboration with a strong network of GPs during previous studies which assures the feasibility of the study [8, 9]. These regions have also been chosen to assure representativeness regarding differences in antibiotic prescription practices [37]

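### The 80% power stated for non-inferiority on days of restricted activity is reached only at one-sided 5% with almost no GP clustering, and section 11.2 states neither assumption

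*Combined protocol and SAP*

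**What the plan says.** Section 11.2 sets the size of the trial: "A study sample of 14 GPs and 15 patients per GP in each arm (210 patients per arm and a total of 630 patients"). For antibiotic prescription it claims 80% power "with 5% level of significance", "when adjusting for clustering at practice level (intracluster coefficient 0.06").

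The next sentence turns to days of restricted activity and says that the same sample size "guarantees a power of 80% to prove non-inferiority in terms of duration of activities restriction (non-inferiority margin=1 day, standard deviation=4 days"). That sentence gives no significance level, no sidedness, no intracluster coefficient and no statement of which arms are compared. The section then refers to simulations in Figure 4, which is not reproduced in the copy available for this review.

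Section 6.2, under methods of minimising bias, gives a general assurance: "The cluster effect related to GP was taken into account while calculating the sample size and the outcome measures". Section 11.1 includes in the alternative hypothesis "no difference in terms of clinical outcome, duration of the episode, activities restrictions and adverse outcomes". Section 11.4 plans a linear mixed effect regression for days of restricted activity and lists no covariates for it.

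**The concern.** A margin of 1 day against a standard deviation of 4 days is a standardised margin of 0.25. With individually randomised patients that needs roughly 200 to 250 per arm for 80% power, depending on the one-sided level. The trial has 210 per arm, so there is almost nothing in reserve for a design effect, yet GPs are randomised and each brings 15 patients.

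Restricted activity is one of only two outcomes for which section 11.2 quantifies non-inferiority. The other, the composite adverse outcome, is a separate matter and is not assessed here. If the algorithms reduce prescribing, this result is part of the evidence that the reduction did not slow patients' return to normal life. A reader who takes 80% at face value expects a harmless algorithm to miss the non-inferiority criterion one time in five. If the real chance of missing it is materially higher, an inconclusive result could be misread as a sign of harm from a well-powered test.

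**Working it through.** **Inputs from the protocol.** 14 GPs × 15 patients = 210 per arm; margin 1 day; SD 4 days; stated power 80% (all section 11.2). True difference 0 (section 11.1). Coefficient 0.06, given for prescribing only (section 11.2).

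**Assumptions, because the text is silent.** Comparison of two arms; one-sided level of either 5% or 2.5%; a range of coefficients for restricted days; no loss to follow-up. Section 11.5 expects some loss but gives no rate, and section 11.2 shows no allowance for it.

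**Formulas.** Design effect DE = 1 + (15 − 1) × ICC. SE = 4 × √(2 × DE / 210). Power = Φ(1/SE − z), with z = 1.645 (one-sided 5%) or 1.960 (one-sided 2.5%).

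**Step 1: reproduce the stated figure.** With ICC = 0, SE = 4 × √(2/210) = 0.390 and 1/SE = 2.562.

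- One-sided 5%: Φ(2.562 − 1.645) = Φ(0.917) = 82.0%. A t-test with 418 df gives 81.9%; a t-test on GP means with 26 df gives 80.2%.
- One-sided 2.5%: Φ(2.562 − 1.960) = Φ(0.602) = 72.6%.

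The 80% is therefore reproduced with independent patients at one-sided 5%, and not at one-sided 2.5%.

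**Step 2: patients needed without clustering.**

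- One-sided 5%: 2 × (4 × (1.645 + 0.842))² ≈ 198 per arm.
- One-sided 2.5%: 2 × (4 × (1.960 + 0.842))² ≈ 252 per arm, already more than 210.

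**Step 3: largest coefficient compatible with 80%.**

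- One-sided 5%: DE can be at most 210/197.8 = 1.061, so ICC ≤ 0.061/14 ≈ 0.004.
- One-sided 2.5%: DE would have to be 210/251.2 = 0.836, which is below 1, so no coefficient of zero or more will do.

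**Step 4: power over an assumed range of coefficients.**

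| ICC | DE | SE (days) | Power, one-sided 5% | Power, one-sided 2.5% |
|---|---|---|---|---|
| 0 | 1.00 | 0.390 | 82.0% | 72.6% |
| 0.01 | 1.14 | 0.417 | 77.5% | 67.0% |
| 0.02 | 1.28 | 0.442 | 73.2% | 62.0% |
| 0.03 | 1.42 | 0.465 | 69.3% | 57.5% |
| 0.06 | 1.84 | 0.530 | 59.6% | 47.2% |

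**Step 5: cross-check.** A simulation of 14 against 14 GP means (40,000 runs) at ICC 0.06 gave 59.8% and 47.8% with normal limits, and 57.6% and 44.2% with 26-df t limits. The normal approximation in the table is slightly generous for this number of GPs.

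**The case against.** The strongest reply is that section 6.2 says clustering was taken into account, that section 11.2 adjusts for it in the sentence just before, and that the simulations behind the figure are in Figure 4, which cannot be seen here. This stands to the extent that a reader might infer from the reproduction that clustering was ignored, and the documents do not show that. A small non-zero coefficient, up to about 0.004 at one-sided 5%, fits the stated 80% as well. The missing figure is not held against the plan. But no simulation of a two-arm comparison with the stated size, margin and SD can give 80% under material clustering. If Figure 4 rests on other inputs, the text should name them.

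Second, a reader might take 47–60% as the true power because 0.06 is the only coefficient in the protocol. The documents do not support that. The value is attached to prescribing, which is the GP's own decision, whereas restricted days are reported by patients, and nothing says the two share a coefficient. At 0.01 and one-sided 5% the shortfall is only two to three points. The 47% also needs one-sided 2.5%, while the only level in section 11.2 is 5%, without sidedness.

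Third, the arms compared are not stated. Pooling both intervention arms against usual care (420 against 210) at one-sided 5% would keep 80% up to a coefficient of about 0.03: SE = 4 × √(1.5 × DE/210) must not exceed 1/2.487 = 0.402, so DE ≤ 1.415. Nothing in the plan provides for such pooling, and at 0.06 it gives 70% (one-sided 5%) or 59% (one-sided 2.5%).

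Finally, this is a secondary outcome and its planned mixed model handles clustering, so the validity of the analysis is not in question. That is correct: the point concerns the stated power.

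**Conclusion.** The statement is wrong as written. For a two-arm comparison with zero true difference, 210 patients per arm, a 1-day margin and an SD of 4 days do not guarantee 80% power. They deliver it only at one-sided 5% together with a coefficient of about 0.004 or less, and section 11.2 states neither. At one-sided 2.5% the figure is out of reach even without clustering. From a coefficient of 0.01 upwards every case in the table is below 80%, by a small amount at 0.01 with one-sided 5% and by 20 to 33 points at 0.06.

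It does not follow that non-inferiority would probably fail for a harmless algorithm. Power drops below one half only in the corner case of 0.06 with one-sided 2.5%; in the other cases tabulated, success remains the more likely result. The conclusion rests on a two-arm comparison, no covariate adjustment and no loss to follow-up. Loss would lower the effective sample and is not allowed for in these figures.

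**What to change.** In section 11.2, remove the word *guarantees* for this outcome. State the one-sided level of the non-inferiority test, which arms are compared, and the intracluster coefficient assumed for days of restricted activity, with its source or an admission that it is assumed. Replace 80% with the cluster-adjusted power that follows. If no coefficient can be justified, give a range such as the one tabulated above and label 0.06 as borrowed from prescribing. If Figure 4 already contains these assumptions, carry them into the text so that it agrees with section 6.2.

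This is a change of wording in the protocol and analysis plan. It needs no extra patients, GPs or procedures. The cost is a less favourable stated figure for this outcome.
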